6.3 Management of Infusion-Related Reactions

IRRs can occur with GEN3009 administration. All patients must receive premedication for IRRs as described in Section [6.2.1](#).

Table 24 GEN3009 Dose Modification Rules for IRRs

IRR Grade	Dose Modification
Grade 1 or 2	
Stop GEN3009 infusion immediately and treat the subject based on local institutional guidelines.Once reaction symptoms resolve, resume the infusion at no more than half the rate at which the IRR occurred.If the subject does not experience any further IRR symptoms, infusion rate escalation may resume at increments and intervals as clinically appropriate. 
Please refer to Section 6.2.1 for premedication instructions.

Grade 3	
Stop GEN3009 infusion immediately and treat the subject based on local institutional guidelinesOnce reaction symptoms resolve, resume the infusion at no more than half the rate at which the IRR occurred.If the subject does not experience any further IRR symptoms, infusion rate escalation may resume at increments and intervals as clinically appropriate.If, after resumption of the infusion, symptoms return (irrespective of grade), permanently discontinue administration of GEN3009 and manage the IRR symptoms accordingly. 
Please refer to Section 6.2.1 for premedication instructions.

Grade 4 (life-threatening)	
Permanently discontinue administration of GEN3009 and institute appropriate emergency care.

Trained trial staff should be prepared to intervene in case of any IRRs occurring, with resources necessary for resuscitation (eg, agents such as epinephrine and aerosolized bronchodilator, also medical equipment such as oxygen tanks, tracheostomy equipment, and a defibrillator) available.

6.4 Dosage(s) and Administration

6.4.1 GEN3009 Monotherapy Cohorts

GEN3009 will be administered as an IV infusion according to the following schedule until 1 or more of the discontinuation criteria in Section 8.1 are met:

- Cycles 1 through 3: Days 1*, 8, 15, and 22 (once weekly for a 28-day cycle)
- Cycles 4 through 9: Days 1 and 15 (every 2 weeks for a 28-day cycle)
- Cycle 10 and beyond: Day 1 (every 4 weeks for a 28-day cycle)

*At dose levels \geq CCI mg, the first dose of GEN3009 can be split into 2 consecutive days (eg, CCI mg at C1D1 and remaining amount at C1D2) after approval of the sponsor's medical monitor.

Refer to the GEN3009 investigational medicinal product (IMP) manual for additional information and guidance on dosage and administration.

Refer to Section 6.6 for information regarding concomitant therapy. Detailed dose modification guidance is provided in Section 7.

In the Dose Escalation, the DLs will be determined by the starting dose and the escalation steps taken in the trial (refer to Section 4.1.1).

During the Dose Escalation, all subjects must remain at the clinic for at least 4 hours after each GEN3009 administration in Cycle 1. Subjects must be instructed to contact the investigator should signs or symptoms of IRRs occur following discharge from the 4-hour observation period. An

observation of up to 24 hours postdose during Cycle 1 is permissible at the discretion of the investigator.

During the Expansion (including safety run-in), all subjects are required to remain at the clinic for at least 2 hours after the GEN3009 administration in Cycle 1. Subjects must be instructed to contact the investigator should signs or symptoms of IRRs and/or CRS (eg, fever, lightheadedness, shortness of breath, etc) occur following discharge.

6.4.2 GEN3009 + GEN3013 Combination Cohort

GEN3009 will be administered as an IV infusion and GEN3013 will be given as an s.c. injection.

A lead-in dose of GEN3009 will be given 7 days prior to the GEN3009 + GEN3013 combination. A step-up dosing of GEN3013 will be used to further reduce the risk of CRS: 0.16 mg on Day 8 of Cycle 1, 0.8 mg on Day 15 of Cycle 1, then 48 mg on Day 22 of Cycle 1 followed by 48 mg for the rest of the cycles.

On the days when both treatments were given, GEN3013 will be administered at least 1 hour prior to the GEN3009 infusion.

In the safety run-in, 2 DLs of GEN3009 (ie, **CC1** mg and RP2D) and 1 DL of GEN3013 (ie, 48 mg) will be tested. Detailed dosing and schedule are shown in [Table 21](#).

After safety and tolerability of GEN3009 + GEN3013 in combination have been evaluated in the safety run-in, the Expansion of the combination will be opened to further evaluate the preliminary anti-tumor activity of GEN3009 at the recommended dose with GEN3013 at 48 mg in R/R DLBCL.

Refer to the IMP manual for additional information and stepwise guidance on dosage and administration.

Refer to Section [6.6](#) for information regarding concomitant therapy. Detailed dose modification guidance is provided in Section [7](#).

In the GEN3009 + GEN3013 combination cohort, all subjects are required to remain at the clinic for at least 2 hours after the GEN3009 infusion in Cycle 1. Subjects must be instructed to contact the investigator should signs or symptoms of IRRs and/or CRS (eg, fever, lightheadedness, shortness of breath, etc) occur following discharge. In addition, all subjects must be hospitalized for mandatory CRS monitoring for at least 24 hours after the third dose (first full dose) at Cycle 1 Day 22 of GEN3013 (ie, 48 mg). Additional or longer hospitalization are based on the investigator's discretion.

6.5 Treatment Compliance

All trial medications will be administered by site personnel to assure compliance with trial requirements.

6.6 Concomitant Medications and Therapies

6.6.1 Permitted Concomitant Medications and Therapies

Investigators may prescribe concomitant medications or treatments deemed necessary to provide adequate supportive care except for those medications identified as "prohibited" (Section [6.6.2](#)).

The following concomitant medication and therapies are permitted during the trial:

- Local palliative radiotherapy on non-target lesions is allowed.
- G-CSF and other hematopoietic growth factors may be used in the management of acute toxicity, such as febrile neutropenia and neutropenia, when clinically indicated or at the investigator's discretion. In case of \geq Grade 3 neutropenia, use of growth factors is mandated in the Dose Escalation and Safety Run-in parts of the study.
- Blood cell transfusion is allowed if clinically indicated.
- Intravenous immunoglobulin (IVIg) is permitted, if clinically indicated.
- Multivitamins, vitamin D, calcium, and supplements in prevention of weight loss. Prescribed medicinal cannabinoids as palliative therapy are allowed.
- Anti-hypertensives are allowed as concomitant medications. However, due to the transient hypotension observed in the monkey toxicology study, consider withholding anti-hypertensive medication for 12 hours prior to infusions.

The sponsor's medical monitor/designee should be contacted if there are any questions regarding concomitant medication or prior therapy. Refer to Section [7.4.3](#) for additional guidance on permitted/required treatments for toxicity management.

The trial site will supply supportive medications, eg, premedication, anti-viral medication, anti IL-6R. Immediate access to tocilizumab is mandated on site.

6.6.1.1 Antibiotic, Antiviral, and Antifungal Therapy

Prophylactic antibiotic, antiviral and antifungal therapies are allowed. For subjects who are considered to have an increased risk for herpes and/or *Pneumocystis jiroveci* infections, prophylaxis is recommended, unless medically contraindicated. For subjects who are considered to have an increased risk for other infections, prophylactic therapy is recommended, unless medically contraindicated.

For subjects with a history of recurrent herpes virus infections, herpes infection during previous anti-lymphoma therapy, neutropenia and/or low CD4+ cell counts (<200 cells/ μ L) prophylactic antiviral therapy is mandatory, eg, acyclovir 400 mg 3 times a day PO. Prophylaxis against *P. jiroveci*, eg, oral trimethoprim/sulfamethoxazole 160 mg/800 mg every other day is mandatory to subjects who are considered at increased risk, eg, subjects with low CD4+ cell counts (<350 cells/ μ L).

Cytomegalovirus reactivation during treatment should be treated according to local standards or available guidelines (O'Brien et al., 2006).

6.6.1.2 Immunizations

For subjects treated with GEN3009 and/or GEN3013, physicians should review the subject's vaccination status and subjects should, if possible, be brought up to date with all immunizations in agreement with current immunization guidelines prior to initiating treatment. Administer vaccines at least 4 weeks prior to start of treatment.

6.6.1.3 Immunoglobulin Therapies

Immunoglobulins administered at doses on the order of 1 g/kg body weight have the potential to alter the clearance of other antibodies. Investigators should therefore be aware that the efficacy of GEN3009 and/or GEN3013 may be decreased when administering immunoglobulins at these doses, for example for the treatment of immune thrombocytopenia, or other immune, inflammatory, or paraneoplastic conditions.

6.6.2 Prohibited Concomitant Therapy

The following medications are prohibited during the trial:

- Any anti-lymphoma therapy, eg, chemotherapy, radiotherapy or experimental therapy or other investigational drugs

Note: Local palliative radiotherapy for pain relief may be allowed after discussion with the sponsor's medical monitor. Irradiated site cannot be used as measurable, target lesions when assessing response to treatment.

- Corticosteroid that exceed a total daily dose of 10 mg of prednisone or equivalent administered for more than 10 days unless for the management of AEs (eg, excluding corticosteroids given as premedication or CRS management)
- Herbal preparations or related OTC preparations containing herbal ingredients are not permitted during participation in the trial
- The use of live, attenuated vaccines is not allowed through the entire duration of trial. Killed virus vaccines are allowed. Note: SARS-CoV-2 vaccine is generally permitted, including mRNA-based, protein-based, or non-replicating viral vector-based vaccines. Consider choosing an appropriate type of SARS-CoV-2 vaccine and consult with an infectious disease expert if desired. **SARS-CoV-2 vaccine should not be administered during the DLT observation period.**
- Investigational agents

If a subject receives any of these during the trial, the sponsor must be notified for evaluation of whether the subject can continue treatment in the trial.

6.7 Investigational Medicinal Product Information

6.7.1 GEN3009 Information

GEN3009 is intended for administration by the IV route after dilution.

6.7.1.1 Physical Description of GEN3009

GEN3009 is supplied at **CC** mg/mL by the sponsor.

6.7.1.2 Packaging and Labeling

GEN3009 labels will contain information to meet the applicable regulatory requirements. For further details see the trial-specific IMP manual.

6.7.1.3 Preparation, Handling, and Storage

GEN3009 must be stored at controlled temperatures ranging from 2°C to 8°C (35.6°F to 46.4°F).

GEN3009 must be prepared aseptically at the site pharmacy. Refer to the IMP manual for additional guidance on trial drug preparation, handling, and storage.

6.7.2 Epcoritamab (GEN3013) Information

Epcoritamab (GEN3013) is to be administered as an s.c. injection by qualified site personnel. Injection site is preferably in the lower part of the abdomen or the thigh. Change of injection site from left or right side or vice versa is recommended especially during weekly administration.

6.7.2.1 Physical Description of Epcoritamab (GEN3013)

Epcoritamab (GEN3013) is supplied at 5 mg/mL or 60 mg/mL by the sponsor.

6.7.2.2 Packaging and Labelling

Epcoritamab (GEN3013) labels will contain information to meet the applicable regulatory requirements. For further details see the trial-specific IMP manual.

6.7.2.3 Preparation, Handling, and Storage

Epcoritamab (GEN3013) must be stored in a refrigerator at 2°C to 8°C (35.6°F to 46.4°F) until use.

Epcoritamab (GEN3013) is supplied as a concentrate for solution for s.c. injection. Priming and intermediate doses of epcoritamab must be diluted at the site/pharmacy using aseptic techniques. Detailed dose preparation instructions including the important dilution steps will be provided in the IMP manual.

6.7.3 Drug Accountability

The investigator or designee must maintain an accurate record of the shipment and dispensing of trial drug in a drug accountability log. Drug accountability will be verified by the field monitor during site visits and at the completion of the trial. At trial close-out, and as appropriate during the trial, the investigator is to destroy all used and unused GEN3009 and/or epcoritamab (GEN3013), packaging, and drug labels, as per local regulations. A copy of the completed drug accountability log and documentation of drug destruction must be provided to the monitor or to the address provided in the investigator folder (unless otherwise agreed with sponsor).

6.8 Technical Complaint Handling

A technical complaint is defined as any suspicion of a product defect related to manufacturing, labeling, or packaging, ie, any dissatisfaction relative to the identity, quality, durability, or reliability of a product, including its labeling or package integrity. A technical complaint may have an impact on the safety and efficacy of the product. Timely, accurate, and complete reporting and analysis of technical complaint information from trials are crucial for the protection of subjects, investigators, and the sponsor, and are mandated by regulatory agencies worldwide. The sponsor has established procedures in conformity with regulatory requirements worldwide to ensure

appropriate reporting of technical complaint information; all trials conducted by the sponsor or its affiliates will be conducted in accordance with those procedures.

6.8.1 Procedures

All initial technical complaints must be reported to the sponsor by the trial-site personnel within 24 hours after being made aware of the event.

If the defect is combined with an AE, the trial-site personnel must report the AE to the sponsor according to the AE and SAE reporting process and timelines (Section [10.4](#)) in addition to reporting the technical complaint. A sample of the suspected product should be maintained for further investigation if requested by the sponsor.

6.8.2 Contacting Sponsor Regarding Product Quality

The names (and corresponding telephone numbers) of the individuals who should be contacted regarding technical complaint issues are listed on the contact information page(s), which will be provided as a separate document.

7 DOSE MODIFICATIONS AND SAFETY MANAGEMENT GUIDELINES

7.1 Dose-limiting Toxicities

7.2 Dose Escalation: Dose-limiting Toxicity

For the Dose Escalation, the DLT assessment period is defined as 28 days from the start of the first GEN3009 administration on C1D1.

The occurrence of any of the toxicities outlined in this section will be considered a DLT.

All Grade 5 toxicities

Hematologic:

- Thrombocytopenia Grade 4 ($<25.0 \times 10^9/\text{L}$ [$<25,000/\mu\text{L}$]) that is not due to underlying malignancy or extraneous cause
- Neutropenia Grade 4 ($<0.5 \times 10^9/\text{L}$ [$<500/\mu\text{L}$]) lasting >7 days **not attributable to underlying disease**
- Febrile neutropenia Grade 3 or 4 lasting >2 days (ie, absolute neutrophil count [ANC] $<1.0 \times 10^9 \text{ cells/L}$ with a single temperature of $>38.3^\circ\text{C}$ [100.9°F] or a sustained temperature of $\geq 38^\circ\text{C}$ [100.4°F] for more than 1 hour)
- Grade 3 or 4 hemorrhage associated with thrombocytopenia of \geq Grade 3 requiring platelet transfusion
- Anemia Grade 4.
- TLS Grade 4 (see [Appendix 4](#) for additional information)

Non-hematologic:

- All non-hematological AEs of grade ≥ 3 (severe or life-threatening), **excluding** the following:
 - a. Fever Grade 3 ($>40.0^\circ\text{C}$ [$>104.0^\circ\text{F}$]) for ≤ 24 hours
 - b. Hypotension Grade 3 (medical intervention indicated; hospitalization indicated) resolving in ≤ 24 hours
 - c. Laboratory values out of normal range that do not have any clinical consequence, are clinically transient in nature and that resolve in ≤ 3 days (including electrolyte abnormalities that respond to medical intervention)
 - d. Aspartate aminotransferase (AST) and/or alanine aminotransferase (ALT) Grade 3 returning to Grade 1 or baseline in ≤ 7 days
 - e. Nausea Grade 3 that responds to adequate antiemetic treatment in ≤ 3 days
 - f. Vomiting Grade 3 that responds to adequate antiemetic treatment in ≤ 3 days
 - g. Diarrhea Grade 3 that responds to adequate antidiarrheal treatment in ≤ 3 days
 - h. Fatigue/asthenia Grade 3 when fatigue/asthenia was present at baseline or that lasts for <14 days
 - i. Alopecia (no grading)

Frequent laboratory monitoring of complete blood count including differential should be initiated to document start and resolution of hematological AEs. All AEs occurring during the defined DLT evaluation period will be assessed according to the criteria above. All AEs, including those not qualifying for a DLT, will be monitored and included in the evaluation of the toxicity profile of GEN3009 unless the event is clearly determined to be unrelated to GEN3009.

7.3 Safety Run-in for Expansion: Dose-limiting Toxicity

For the Expansion GEN3009 + GEN3013 combination cohort safety run-in, the DLT assessment period is defined as 28 days from the start of the first GEN3009 administration on C1D1.

The occurrence of any of the toxicities outlined in this section will be considered a DLT.

All Grade 5 toxicities

Hematologic:

- Thrombocytopenia Grade 4 ($<25.0 \times 10^9/\text{L}$ [$<25,000/\mu\text{L}$]) lasting >7 days not attributable to underlying disease
- Neutropenia Grade 4 ($<0.5 \times 10^9/\text{L}$ [$<500/\mu\text{L}$]) lasting >7 days not attributable to underlying disease
- Febrile neutropenia Grade 3 or 4 lasting >2 days (ie, ANC $<1.0 \times 10^9$ cells/L with a single temperature of $>38.3^\circ\text{C}$ [100.9°F] or a sustained temperature of $\geq 38^\circ\text{C}$ [100.4°F] for more than 1 hour)
- Grade 3 or 4 hemorrhage associated with thrombocytopenia of \geq Grade 3 requiring platelet transfusion
- Anemia Grade 4
- TLS Grade 4 (see [Appendix 4](#) for additional information)

Non-hematologic:

- All non-hematological AEs of Grade ≥ 3 (severe or life-threatening), excluding the following:
 - a. CRS Grade 3 according to American Society for Transplantation and Cellular Therapy (ASTCT) criteria ([Lee et al., 2019](#)), which has improved to Grade ≤ 2 or resolved (Grade 0) within 48 hours
 - b. ICANs Grade 3 according to ASTCT criteria ([Lee et al., 2019](#)), which has improved to Grade ≤ 2 or resolved (Grade 0) within 48 hours
 - c. Fever Grade 3 ($>40.0^\circ\text{C}$ [$>104.0^\circ\text{F}$]) for ≤ 24 hours (this applies to fever not considered a symptom of other toxicities such as CRS)
 - d. Hypotension Grade 3 (medical intervention indicated; hospitalization indicated) resolving in ≤ 24 hours (this applies to hypotension not considered a symptom of other toxicities such as CRS)
 - e. Laboratory values out of normal range that do not have any clinical consequence, are clinically transient in nature and that resolve in ≤ 7 days (including electrolyte abnormalities that respond to medical intervention)
 - f. AST and/or ALT Grade 3 returning to Grade 1 or baseline in ≤ 7 days

- g. Nausea Grade 3 that responds to adequate antiemetic treatment in ≤ 3 days
- h. Vomiting Grade 3 that responds to adequate antiemetic treatment in ≤ 3 days
- i. Diarrhea Grade 3 that responds to adequate antidiarrheal treatment in ≤ 3 days
- j. Fatigue/asthenia Grade 3 when fatigue/asthenia was present at baseline or that lasts for <14 days
- k. Alopecia (no grading)

Frequent laboratory monitoring of complete blood count including differential should be initiated to document start and resolution of hematological AEs. All AEs occurring during the defined DLT evaluation period will be assessed according to the criteria above. All AEs, including those not qualifying for a DLT, will be monitored and included in the evaluation of the toxicity profile of GEN3009 in combination with GEN3013 unless the event is clearly determined to be unrelated to GEN3009 and/or GEN3013.

7.4 Dose Modification Guidance and Safety Stopping Criteria

7.4.1 Dose Escalation Part (GEN3009 Monotherapy)

If a subject experiences a DLT, the subject may continue treatment with GEN3009, if the toxicity recovers to \leq Grade 2 or baseline within 4 weeks from occurrence of the DLT. Continued administration of GEN3009 must be agreed to between the sponsor and the investigator based on a thorough assessment of the event, the duration of the event, and benefit-risk for the subject. In the event a subject experiences a second episode of a DLT with GEN3009, the treatment will be permanently discontinued. Treatment with GEN3009 will be discontinued in the event the DLT is not resolved within 4 weeks.

- If a subject experiences toxicity that qualifies as a DLT but occurs after the 4-week DLT evaluation period, the subject's benefit-risk must be thoroughly assessed. Continued treatment with GEN3009 must be agreed between the sponsor and the investigator.
- For the subject who receives more than 4 doses of GEN3009, ie, treatment beyond the DLT evaluation period, all corresponding AEs that meet the DLT criteria will be considered for the purpose of determining the MTD and/or the RP2D. For the declaration of the RP2D of GEN3009 in the Expansion and for further development, the totality of the data from Dose Escalation (including safety, PK, pharmacodynamics, and preliminary efficacy will be evaluated).
- During the trial, a planned dose of GEN3009 can be postponed for up to 4 weeks from the last dose of trial drug for an AE whether it is considered drug-related or not.
- In case of dose delay of more than 4 weeks from the last trial drug administration due to toxicity, GEN3009 should be discontinued, unless approved by the sponsor's medical monitor.
- During the trial, the GEN3009 dose can be held for the following laboratory results:
 - a. If platelet count $<50 \times 10^9/L$, hold dose until platelet count is $\geq 50 \times 10^9/L$.
 - b. If febrile neutropenia $<0.5 \times 10^9/L$, hold dose until neutrophil count is $\geq 0.5 \times 10^9/L$.
 - c. If hemoglobin is <8 g/dL (<5 mmol/L), hold dose until hemoglobin ≥ 8 g/mL (>5 mmol/L).

Note: If the investigator deems any of the above cytopenia as bone marrow involvement due to the disease, continuation of GEN3009 treatment can be discussed with the sponsor's medical monitor. Transfusion with blood products and/or administration with G-CSF is permitted if needed (refer to Section [6.6.1](#)).

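### In Dose Escalation, a second Grade 3 infusion reaction inside the 28-day DLT window gets opposite instructions: Section 7.4.1 says stop for good, Table 24 says resume

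*Protocol*

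**What the plan says.** Protocol Section 7.2 sets the DLT window for Dose Escalation at 28 days from the first GEN3009 dose. Among the qualifying toxicities are "All non-hematological AEs of grade" 3 or higher, less a list of exclusions (a to i). IRR is not on that list. Grade 3 fever and Grade 3 hypotension lasting 24 hours or less are.

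Section 7.4.1 then governs what happens to the subject. After a first DLT: "If a subject experiences a DLT, the subject may continue treatment with GEN3009, if the toxicity recovers to" Grade 2 or baseline within 4 weeks, and "Continued administration of GEN3009 must be agreed to between the sponsor and the investigator based on a thorough assessment of the event". After another: "In the event a subject experiences a second episode of a DLT with GEN3009, the treatment will be permanently discontinued". For DLT-type toxicity after the 4-week period, the same section asks only for a benefit-risk assessment and agreement.

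Section 6.3, Table 24, covers IRRs and is not restricted to one part of the trial. For Grade 3 the site stops the infusion and treats. Then: "Once reaction symptoms resolve, resume the infusion at no more than half the rate at which the IRR occurred". The only trigger for discontinuation in that row is: "If, after resumption of the infusion, symptoms return (irrespective of grade), permanently discontinue administration of GEN3009 and manage the IRR symptoms accordingly". For Grade 4 the instruction is: "Permanently discontinue administration of GEN3009 and institute appropriate emergency care".

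The infusion days are in Section 6.4.1: "Cycles 1 through 3: Days 1*, 8, 15, and 22 (once weekly for a 28-day cycle").

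**The concern.** Table 24 is what a site will use while a reaction is in progress. Its Grade 3 row mentions neither DLT status nor Section 7.4.1, and it does not ask whether the subject has reacted before. A site following it at a second Grade 3 IRR in Cycle 1 would restart the infusion in the same session. Section 7.4.1 would by then have ended that subject's treatment.

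What is at stake is re-exposure of a subject after two severe reactions in a first-in-human trial, and a protocol deviation by a site that believed it was following the protocol.

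**Working it through.** No planned figure is in dispute. The check traces one case through the rules and then bounds how often it could arise.

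**Rule trace.** The case is a Grade 3 IRR on Day 1 that resolves, followed by a second Grade 3 IRR at a later, separate infusion.

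1. *Is each reaction a DLT?* Section 10.1.4 has IRRs judged as related, which meets the relatedness condition for DLTs in SAP Section 11.1.1. Section 10.2.2 has the diagnosis recorded rather than its symptoms. IRR is not excluded in 7.2, so a Grade 3 IRR qualifies. The exception is a reaction that amounts only to the excluded fever or hypotension. Section 7.2 lacks the wording in 7.3 that limits those exclusions to events that are not symptoms of another toxicity.
2. *Is the second reaction inside the window?* As scheduled, yes: the Cycle 1 infusions are on Days 1, 8, 15 and 22, all before Day 28. After a Day 1 event, 4 − 1 = 3 scheduled infusions remain. Three is a maximum, because 7.4.1 allows a dose to be postponed up to 4 weeks from the last one. After a Day 1 dose that reaches Day 1 + 28 = Day 29, which is outside the window.
3. *What does each rule say at the second event?*

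| Event | Section 7.4.1 | Table 24, Grade 3 row |
|---|---|---|
| First Grade 3 IRR | May continue with recovery and sponsor-investigator agreement | Resume at half rate or less once resolved; agreement not mentioned |
| Symptoms return after that restart | – | Discontinue permanently |
| Second Grade 3 IRR, later infusion, in window | Discontinue permanently | Resume at half rate or less once resolved |
| Same event, after the window | Benefit-risk assessment and agreement | Resume at half rate or less once resolved |

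The third row is the direct contradiction.

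4. *Does any text give precedence?* No. Section 6.4.1 points to Section 7 for dose modification, and Section 7.4.3 points back to Section 6.3.

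**Frequency.** The inputs are in Section 2.1.4.1.

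- Subjects evaluated for DLTs: 1 + 1 + 1 + 4 + 4 + 4 + 3 = 18, with 0 DLTs.
- IRRs: 61.1% of 18, that is 11/18, mostly Grade 1 or 2 and at the first infusion.
- Exact upper limit for 0/18, one-sided 95%: 1 − 0.05^(1/18) = 0.153.
- Upper end of the two-sided 95% interval: 1 − 0.025^(1/18) = 0.185.

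These limits bound a first DLT of any kind. Two Grade 3 IRRs in one subject cannot be more frequent than one DLT, so the same limits hold and the true rate is likely well below them.

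**Effect on dose finding.** Table 22 counts subjects with DLTs, not episodes, so a second DLT in the same subject changes nothing. Section 11.1.2 keeps a subject with a Cycle 1 DLT in the dose-determining set, and one who stops for toxicity stays in whatever dose was received.

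**The case against.** The strongest reply is that the two rules work at different levels. Table 24 handles one infusion; 7.4.1 is a subject-level rule written for Dose Escalation. Section 7.2 requires every AE in the window to be assessed against the DLT criteria, and 6.4.1 sends sites to Section 7. A site doing all this would stop. It would also already have sponsor agreement from the first event, so it would have to overlook 7.4.1 twice to go wrong. Much of this stands and is why the point is minor. It does not remove the contradiction, because the protocol nowhere tells the site to let 7.4.1 override Table 24.

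A second reply is that a reaction at a later infusion counts as symptoms returning after resumption, so Table 24 would itself require a stop. The wording does not support this. It refers to the infusion that was interrupted. Applied across infusions, irrespective of grade, it would end treatment for a Grade 1 reaction on Day 8 after a resolved Grade 3 on Day 1, although the Grade 1 or 2 row says to resume. Section 6.2.1 expects dosing to go on into Cycle 2 after a Cycle 1 Grade 3 IRR. Where the protocol counts episodes it does so openly: Table 26 has a row for a second Grade 3 CRS event, and Table 28 separates first from second episodes.

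A reader might also infer more than the documents support:

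- *That Grade 4 reactions are in conflict too.* They are not. Section 7.4.1 conditionally permits continuation and Table 24 requires a stop, so stopping satisfies both.
- *That restarting in the same session after a first Grade 3 IRR breaches 7.4.1.* The text does not say that finishing the interrupted infusion needs prior agreement. The assessment that 7.4.1 describes fits the decision on the next scheduled dose.
- *That a second event in any later cycle gets the same treatment.* After the window, 7.4.1 no longer mandates discontinuation.

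**Conclusion.** The contradiction is real but narrow. It is confined to Dose Escalation, to a Grade 3 IRR that qualifies as a DLT, and to a second such event at a separate infusion still inside the 28-day window. There, 7.4.1 and the Grade 3 row of Table 24 give opposite instructions with no stated order of precedence. This rests on reading Table 24 per infusion, which is how it is worded.

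It is probably rare. The 15.3% and 18.5% figures are upper limits on a first DLT, not estimates. They treat the 18 subjects as exchangeable across the doses tested, and higher dose levels have since been added. The agreement required after a first DLT is a further, partial safeguard.

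A reader might infer that the MTD determination is compromised. It is not: DLT counts, the dose-determining set and the mBOIN decisions come out the same whichever instruction the site follows. This is a minor safety and compliance correction.

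**What to change.** Add to the Grade 3 row of Table 24:

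> *Dose Escalation: if the IRR meets the DLT criteria in 7.2 and is the subject's second DLT within the DLT evaluation period, do not resume; permanently discontinue GEN3009 per 7.4.1. After a first such IRR, sponsor-investigator agreement per 7.4.1 is needed before the next scheduled dose.*

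Leave three things as they are: the same-session restart after a first Grade 3 IRR, the post-window rule in 7.4.1, and the Grade 4 row. Requiring agreement before any further GEN3009 would block that restart, which is a clinical change that could leave partial doses and alter exposure. A stop at any infusion, without the window limit, could override the post-window rule.

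The cost is two sentences in one table row. Section 14.1 requires a formal amendment with IEC/IRB approval, so the text can go into the next planned amendment. Meanwhile a note can remind sites that 7.4.1 applies to Grade 3 IRRs in the DLT window. Visits, data collection and analysis do not change.
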